1. PROTOCOL SUMMARY

1.1. Synopsis

Rationale

Atopic dermatitis (AD), also known as atopic eczema, is a common, chronic, inflammatory skin disorder characterized by flaky skin lesions, intense pruritus, and a general deterioration in the quality of life. Over the past 50 years, AD has become more prevalent, especially in industrialized, temperate countries such as the United States (US).^{1,2} Earlier reports indicated that, in up to 70% of cases, the disease greatly improves or resolves until late childhood, however more recent findings suggest that disease activity remains manifest for a prolonged period of time. Based on a total of 7157 patients enrolled in the Pediatric Eczema Elective Registry (PEER) study, comprising a total of 22,550 person-years,³ it was concluded that symptoms associated with AD seem to persist well into the second decade of a child's life and likely longer. At every age, more than 80% of PEER study participants had symptoms of AD and/or were using medication to treat their AD.

There are a limited number of treatments available for AD. Current treatments for AD include emollients, topical corticosteroids (eg, betamethasone, clobetasol, fluocinonide), topical calcineurin inhibitors (eg, pimecrolimus, tacrolimus), and coal tar preparations. Crisaborole was approved as a topical treatment in December 2016 by the Food and Drug Administration (FDA) for use in patients with mild to moderate AD. Additional treatments generally reserved for severe AD include phototherapy (eg, ultraviolet A light [UVA] with or without psoralen, ultraviolet B light [UVB] narrowband or broadband) and systemic agents (eg, corticosteroids, cyclosporine, recombinant interferon [IFN] interferon-gamma [IFN- γ], mycophenolate mofetil, methotrexate [MTX], azathioprine, intravenous [IV] immunoglobulin).⁴ Of the currently available therapies, none offers a cure; therefore, the main aims of existing treatments are to reduce the occurrence of acute flares, to increase the time between relapses, and to reduce pruritus and the resulting sleep disturbance.^{5,6}

Other systemic agents to treat AD are under clinical development or recently approved. Dupilumab, an injectable human monoclonal antibody targeting interleukin (IL) -4 and -13, was approved by the FDA in March 2017 and received marketing authorization in Europe in September 2017, and offers a novel mechanism of action for the treatment of moderate to severe AD. However, the approved dosing for Dupilumab as an initial dose of 2×300 mg subcutaneous injections followed by 300 mg every other week injections may limit the desirability of this route of treatment.

Key cytokines implicated in the pathophysiology of AD including IL-4, IL-5, IL-13, IL-22, IL-31, and IFN- γ require Janus kinase 1 (JAK1) for signal transduction; this suggests that selective JAK1 inhibitors that modulate the activity of these cytokines represent a compelling approach to the treatment of inflammatory skin diseases such as AD.⁷

PF-04965842 is an orally bioavailable small molecule that selectively inhibits JAK1 by blocking the adenosine triphosphate (ATP) binding site. PF-04965842 has a high degree of selectivity against other kinases: 28-fold selectivity over JAK2, >340-fold over JAK3 and 43-fold over tyrosine kinase 2 (TYK2), as well as a good selectivity profile over the broader range of human kinases. The selective inhibition of JAK1 will lead to modulation of multiple cytokine pathways involved in the pathophysiology of AD, including IL-4, IL-5, IL-13, IL-31 and IFN- γ . Data from a Phase 2b proof of concept (POC) study (B7451006) that evaluated participants with moderate to severe AD have shown positive efficacy, as well as an acceptable safety profile, sufficient to support further clinical development in a larger Phase 3 program.

Preclinical in vitro inhibition studies showed that the unbound maximum observed concentration $(C_{max})/50\%$ inhibitory concentration (IC50) ratio is 0.24 and 0.13 for multidrug and toxic compound extrusion transporter (MATE)1 and MATE2K, respectively, suggesting that PF-04965842 has a potential to inhibit these drug transporters in vivo as ratios exceed the in vitro regulatory threshold unbound C_{max}/IC_{50} ratio of 0.02.⁸ Therefore, a clinical interaction study with a sensitive MATE1 and MATE2K substrate is needed to assess the effect of PF-04965842 on the activity of these transporters. The primary purpose of this study is to assess the effect of PF-04965842 on the in vivo pharmacokinetics (PK) of metformin, a sensitive substrate for MATE1 and MATE2K.⁸ Metformin is also a substrate for organic cation transporter (OCT)1 and OCT2. However, PF-04965842 is not an inhibitor of OCT2 (C_{max}/IC50 ratio is >300) and despite the unbound PF-04965842 C_{max}/IC50 ratio for OCT1 being just above 0.02 (0.03), inhibition of OCT1, a hepatic uptake transporter, is not expected to increase plasma metformin exposures as OCT1 does not modulate metformin clearance as it is primarily excreted unchanged in urine. Both MATE1 and MATE2K are renal transporters that are expressed in the apical membrane of the renal proximal tubules thus play an important role in tubular secretion and reabsorption of drug molecules in the kidney. Therefore, significant MATE1/2K inhibition would primarily impact the renal clearance of substrates for these transporters with having minimal effects, if any, on plasma exposures.

 N^{1} -methylnicotinamide (NMN), a metabolite of niacin, has been reported to be an endogenous biomarker for assessing MATE/OCT2 inhibition. Renal clearance of NMN was shown to be reduced by ~70% by pyrimethamine, a potent MATE/OCT2 inhibitor.⁹ As such, NMN is being assessed in this study to further investigate the utility of this endogenous substance as a biomarker for MATE activity in comparison to metformin, the gold standard for assessing MATE activity in drug-drug interaction (DDI) studies.⁸

Objectives and Endpoints

Objectives:	Endpoints:
Primary:	Primary:
• To estimate the effect of PF-04965842 on MATE1/2K activity via the pharmacokinetic assessment of a single, oral dose of metformin in healthy participants.	Metformin CL _{r.}
Secondary:	Secondary:
• To evaluate the PK, safety and tolerability of a single oral dose of metformin when co-administered with PF-04965842.	 Metformin AUC_{inf}, C_{max}, T_{max}, AUC_{last}, CL/F, Vz/F, t¹/₂, Ae, and Ae%. Vital signs, laboratory tests and adverse events.
Tertiary/Exploratory:	Tertiary/Exploratory:
• To evaluate the effects of PF-04965842 on N ¹ -methylnicotinamide.	• N ¹ -methylnicotinamide AUC ₂₄ , C _{max} , Ae and CL _r .
• To correlate the effects of PF-04965842 on N ¹ -methylnicotinamide versus metformin.	• Potential results from exploratory analysis of banked biospecimens (these results may or may not be generated in the context of the present
• To enableexploratory research through the collection of banked biospecimens, unless prohibited by local regulations or ethics committee decision.	study).

Overall Design

This is a Phase 1, randomized, 2-way crossover, open label study of the effect of PF-04965842 on metformin PK in healthy adult participants. The effect of PF-04965842 on NMN PK and its correlation to the effect on metformin PK will also be assessed. Participants will be randomized to 1 of 2 treatment sequences as described below. A total of 12 healthy male and/or female participants will be enrolled in the study so that 6 participants will be enrolled in each treatment sequence. Each treatment sequence will consist of 2 periods. Participants who discontinue from the study may be replaced at the sponsor's discretion. The replacement participant will receive the same treatment sequence as the participant who discontinued.

Participants will be screened within 28 days of the first dose of investigational product. Participants will report to the clinical research unit (CRU) the day prior to Day 1 (ie Day -1) dosing in Period 1 for both treatment sequences. In both sequences, participants will remain in the CRU for a total of 8 days and 7 nights (including Period 1 and Period 2). To adequately remove any drug effects of metformin (plasma half-life ~ 6 hours/whole blood half-life ~ 18 hours), there will be a minimum 4-day washout period between metformin dosing events from Period 1 to Period 2. The minimum 3-day washout for PF-04965842 in Sequence 2 is sufficient as the half-life of PF-04965842 is \sim 3-5 hours. The metformin PK will be assessed over 48 hours.

Number of Participants

A total of approximately 12 healthy male and/or female participants will be enrolled in the study so that approximately 6 participants will be enrolled in each treatment sequence.

Intervention Groups and Duration

Sequence	Period 1	Washout	Period 2
Sequence 1 ($N = 6$)	Treatment A	At least 4 days from metformin administration	Treatment B
Sequence 2 (N = 6)	Treatment B	At least 4 days from metformin + PF-04965842 administration ^a	Treatment A

Treatment Sequences

Abbreviations: N = number of enrolled participants; QD = once daily.

Treatment A (Reference): Single oral administration of metformin 500 mg on Day 1.

Treatment B (Test): Concomitant single oral administration of metformin 500 mg on Day 1 and oral administration of PF-04965842 200 mg QD for 2 days on Days 1-2.

a. At least a 3-day washout is required from the last dose of PF-04965842.

• All treatments administered on Day 1 will be administered following a moderate-fat meal. PF-04965842 can be dosed with or without food on Day 2 in Treatment B.

Data Monitoring Committee: No

Statistical Methods

Natural log transformed area under the curve from zero to infinity (AUC_{inf}), area under the plasma concentration-time curve from 0 to the time of last measurement (AUC_{last}), maximum observed concentration (C_{max}) and renal clearance (CL_r) of metformin will be analyzed using a mixed effect model with sequence, period and treatment as fixed effects and participant within sequence as a random effect. Additionally, area under the plasma concentration-time curve from 0 to 24 hours (AUC₂₄), C_{max} and CL_r of NMN will also be analyzed using a mixed effect model with sequence, period and treatment as fixed effects and participant within sequence as a random effect. Estimates of the adjusted mean differences (Test-Reference) and corresponding 90% confidence intervals will be obtained from the model. The adjusted mean differences and 90% confidence intervals for the differences will be exponentiated to provide estimates of the ratio of adjusted geometric means (Test/Reference) and 90% confidence intervals for the ratios. Metformin alone will be the

Reference treatment (Treatment A), while the metformin co-administered with PF-04965842 will be the Test treatment (Treatment B).

A sample size of 12 participants will provide 90% confidence intervals for the difference between treatments of ± 0.134 , ± 0.161 and ± 0.148 on the natural log scale for metformin AUC_{inf}, C_{max} and CL_r, respectively, with 80% coverage probability. The following table presents the width of 90% confidence interval for different estimated effects (Table 4):

Parameter	Estimated Effect (100*Test/Reference)	90% CI	CI Width
CL _r	60%	51.73, 69.60	17.88
	70%	60.35, 81.20	20.85
	80%	68.97, 92.80	23.83
	90%	77.59, 104.40	26.81
	100%	86.21, 115.99	29.79
AUC _{inf}	100%	87.47, 114.32	26.84
	120%	104.97, 137.18	32.22
	160%	139.96, 182.91	42.95
	200%	174.94, 228.63	53.69
C _{max}	100%	85.10, 117.50	32.39
	120%	102.13, 141.00	38.88
	160%	136.17, 188.00	51.83
	200%	170.21, 235.00	64.79

Sample Size Determination

Abbreviation: CI = confidence interval

These calculations are based on estimates of within participant standard deviations of 0.156, 0.188 and 0.173 for log_e AUC_{inf}, log_e C_{max} and log_e CL_r of metformin, respectively, as obtained from internal and/or external data in previous clinical studies with metformin.^{10, 11}

1.2. Schema

Not Applicable.

1.3. Schedule of Activities (SoA)

The SoA table provides an overview of the protocol visits and procedures. Refer to the STUDY ASSESSMENTS AND PROCEDURES section (Section 8) of the protocol for detailed information on each procedure and assessment required for compliance with the protocol.

The investigator may schedule visits (unplanned visits) in addition to those listed in the SoA table, in order to conduct evaluations or assessments required to protect the well-being of the participant.

Table 1.Schedule of Activities

Visit Identifier	Screening			Period 1			Period 2 ^a			ЕТ	Phone call
Days Relative to Day 1	-28 to -2	-1	1	2	3	4	1	2	3		28-35 days after last dose of metformin ^b
Informed Consent	Х										
Inclusion/Exclusion Criteria	Х	Х									
Medical, Drug, Tobacco and Alcohol History	Х										
Complete Physical Examination ^c		Х									
Demography, Height and Weigh	Х										
Serum FSH (Postmenopausal Females Only)	Х										
Serum Pregnancy Test (HCG) for WOCBP only	Х	Х							Х	Х	
Blood sampling for Pfizer Prep D1 banked sample(s) ^d			Х								
Urine Drug Screen	Х	Х									
Single 12-Lead ECG	Х		X ^e				X ^e		Х	Х	
Clinical Safety Labs (Blood and Urine)	Х	Х				Xf			Х	Х	
Contraception check	Х	Х							Х	Х	Х
Serology: HIV, HepBsAg, HepBcAb, HepBsAb, HCVAb testing	Х										
QuantiFERON [®] - TB Gold Test	Х										
Vital Signs and Oral Temperature	Х		X ^g				X ^g		Х	Х	
Moderate Fat Meal consumed prior to dosing			Х				Х				
Metformin Dosing ^h			Х				Х				
PF-04965842 Dosing (Sequence 1)							Х	Х			
PF-04965842 Dosing (Sequence 2)			Х	Х							
Metformin PK Blood Sampling			X ⁱ	\rightarrow	X ⁱ		X ⁱ	\rightarrow	X ⁱ		
Metformin PK Urine Sampling			X ⁱ	\rightarrow	X ⁱ		X ⁱ	\rightarrow	X ⁱ		
NMN PK Blood Sampling			X ⁱ	X ⁱ			X ⁱ	X ⁱ			

Table 1.Schedule of Activities

Visit Identifier	Screening	Period 1		Period 2 ^a			ET	Phone call			
Days Relative to Day 1	-28 to -2	-1	1	2	3	4	1	2	3		28-35 days after last dose of metformin ^b
NMN PK Urine Sampling			X ⁱ	X ⁱ			X ⁱ	X ⁱ			
CRU Confinement		Х	\rightarrow	\rightarrow	\rightarrow	\rightarrow	\rightarrow	\rightarrow	Х		
Serious and non-serious Adverse Event Monitoring	Х	\rightarrow	\rightarrow	\rightarrow	\rightarrow	\rightarrow	\rightarrow	\rightarrow	\rightarrow	\rightarrow	Х
Prior/Concomitant Treatment Assessment	Х	\rightarrow	\rightarrow	\rightarrow	\rightarrow	\rightarrow	\rightarrow	\rightarrow	\rightarrow	\rightarrow	Х

Abbreviations: \rightarrow = ongoing/continuous event; CRU = clinical research unit; ECG = electrocardiogram; ET = early termination; FSH = follicle-stimulating hormone; HepBcAb = hepatitis B core antibody; HepBsAb = hepatitis B surface antibody; HepBsAg = hepatitis B surface antigen; HCVAb = hepatitis C antibody; HCG = Human Chorionic Gonadotropin; HIV = human immunodeficiency virus; hr = hour; NMN = N¹-methylnicotinamide; PK = pharmacokinetic; TB = tuberculosis; WOCBP = women of childbearing potential.

a. Day 1 of Period 2 will be at least 4 days after Day 1 of Period 1.

b. Phone contact to capture any potential AEs and concomitant treatment(s) and to confirm appropriate contraception usage.

c. After the complete physical examination on Day -1, further examinations will be performed at the discretion of the investigator.

d. If not collected on the designated collection day, collect at the next available time point when biospecimens are being collected in conjunction with a participant visit.

e. Perform single 12 lead ECG at pre-dose (before meal) and 2 hours post-dose.

f. Clinical safety labs will be collected before Period 2 Day 1.

g. Supine blood pressure, pulse rate and oral temperature pre dose and 2 hr post dose.

h. Participants will be dosed with metformin following a moderate-fat breakfast at approximately 08:00 AM (±2 hrs). On the day of co administration of metformin and PF-04965842, metformin will be administered with PF-04965842 concomitantly in no specific order, over no more than 5 minutes apart.

i. See pharmacokinetic sampling schema. (Table 2).

Table 2. Pharmacokinetic Sampling Schema

	Periods 1 and 2											
Visit Identifier	Day 1							Da	Day 2			
Hours After Dose on Day 1	0 ^a	0.5	1	2	4	6	8	12	16	24	36	48
Blood samples for												
PK blood sampling for metformin	X ^a	Х	Х	Х	Х	Х	Х	Х	Х	Х	Х	Х
PK blood sampling for NMN	X ^a	Х	Х	Х	Х	Х	Х	Х	Х	Х		
Urine samples for												
Predose PK spot urine blank	X ^a											
Start/Stop PK Urine collection for metformin concentrations ^{b,c}	Х←							\rightarrow X \leftarrow		→Х←	$\rightarrow X \leftarrow$	→Х
Start/Stop PK Urine collection for NMN ^{b,d}	Х←							→Х←		→Х		

Abbreviations: NMN = N1-methylnicotinamide; PK = pharmacokinetic.

a. Predose (metformin administration) sample collection.

b. Each subject will empty his or her bladder just prior to dosing. Then, all urine voids must be collected in appropriate urine collection containers. Each collection interval should have its own collection container(s). At the end of the urine collection interval, the total volume will be measured and recorded. The urine will then be mixed thoroughly. A 5 mL aliquot will be transferred to an appropriately labeled, screw capped polypropylene tube for NMN analysis. A second 5 mL aliquot will also be collected and analyzed for metformin PK concentrations.

c. PK urine collection interval for metformin concentration assessment: 0-12, 12-24, 24-36, and 36-48 hours postdose.

d. PK urine collection interval for NMN concentration assessment: 0-12 and 12-24 hours postdose.

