4.4. End of Study Definition

A participant is considered to have completed the study if he/she has completed all phases of the study including the last contact phone call.

The end of the study is defined as the date of the last scheduled procedure shown in the schedule of activities of the last participant in the study.

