6.1. Study Intervention(s) Administered

For this study, the investigational products are PF-04965842 (provided as 100 mg tablets) and metformin (provided as 500 mg tablets).

PF-04965842 100 mg tablets will be supplied to the CRU in bulk along with individual dosing containers for unit dosing.

Commercially available metformin (GLUCOPHAGE[®]) will be acquired from an external/local supplier as 500 mg tablets. The CRU will ensure that all containers of metformin tablets to be used in the study are from the same lot.

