6.1.1. Administration

Administration of investigational product will be carried out according to the conditions described in the Section 1.3 and Section 5.3.1 of this protocol.

For Treatment A, following consumption of a moderate fat meal (provided 30 minutes prior to administration), participants will receive metformin at approximately 08:00 AM (±2 hours), followed by intake of approximately 240 mL of ambient temperature water.

For Treatment B, following consumption of a moderate fat meal (provided 30 minutes prior to administration), the PF-04965842 200 mg dose and metformin 500 mg dose will be concomitantly administered, in no specific order, over no more than 5 minutes at 08:00 AM \pm 2 hours with ambient temperature water to a total volume of approximately 240 mL. The second dose of PF-04965842 200 mg administered approximately 24 hours after the administration of the first dose will be administered with or without food.

Participants will swallow the investigational product whole, and will not manipulate or chew the investigational product prior to swallowing.

In order to standardize the conditions on PK sampling days, all participants will be required to refrain from lying down (except when required for BP, pulse rate, and ECG measurements), eating, and drinking beverages other than water during the first 4 hours after dosing.

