8. STUDY ASSESSMENTS AND PROCEDURES

Participants will be screened within 28 days prior to administration of the investigational product to confirm that they meet the study population criteria for the study. The investigator (or an appropriate delegate at the investigator site) must obtain a signed and dated ICD before performing any study-specific procedures. If the time between screening and dosing exceeds 28 days as a result of unexpected delays (eg, delayed drug shipment), then participants do not require rescreening if the laboratory results obtained prior to first dose administration meet eligibility criteria.

A participant who qualified for this protocol but did not enroll from an earlier cohort/group may be used in a subsequent cohort/group without rescreening, provided laboratory results obtained prior to the first dose administration meet eligibility criteria for this study. In addition, other clinical assessments or specimen collections, eg, banked biospecimens, may be used without repeat collection, as appropriate.

Study procedures and their timing are summarized in the SoA. Protocol waivers or exemptions are not allowed.

Immediate safety concerns should be discussed with the sponsor immediately upon occurrence or awareness to determine if the participant should continue or discontinue study intervention.

Adherence to the study design requirements, including those specified in the SoA, is essential and required for study conduct.

All screening evaluations must be completed and reviewed to confirm that potential participants meet all eligibility criteria. The investigator will maintain a screening log to record details of all participants screened and to confirm eligibility or record reasons for screening failure, as applicable.

Every effort should be made to ensure that protocol-required tests and procedures are completed as described. However, it is anticipated that from time to time there may be circumstances outside the control of the investigator that may make it unfeasible to perform the test. In these cases, the investigator must take all steps necessary to ensure the safety and well-being of the participant. When a protocol-required test cannot be performed, the investigator will document the reason for the missed test and any corrective and preventive actions that he or she has taken to ensure that required processes are adhered to as soon as possible. The study team must be informed of these incidents in a timely manner.

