8.3.1. Time Period and Frequency for Collecting AE and SAE Information

The time period for actively eliciting and collecting AEs and SAEs ("active collection period") for each participant begins from the time the participant provides informed consent, which is obtained before the participant's participation in the study (ie, before undergoing any study-related procedure and/or receiving investigational product), through and including a minimum of 28 calendar days after the last administration of the investigational product.

For participants who are screen failures, the active collection period ends when screen failure status is determined.

Medical occurrences that begin before the start of study intervention but after obtaining informed consent will be recorded on the Medical History/Current Medical Conditions section of the case report form (CRF), not the AE section.

Follow-up by the investigator continues throughout and after the active collection period and until the event or its sequelae resolve or stabilize at a level acceptable to the investigator, and Pfizer concurs with that assessment.

Investigators are not obligated to actively seek AE or SAE after conclusion of the study participation. However, if the investigator learns of any SAE, including a death, at any time after a participant has been discharged from the study, and he/she considers the event to be reasonably related to the study intervention or study participation, the investigator must promptly notify the sponsor.

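### The final phone call is timed from the last metformin dose, so in Sequence 1 it can fall 27 days after the last PF-04965842 dose, one day short of the protocol's 28-day adverse event minimum.

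*Protocol*

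**What the plan says.** - **Timing of the call.** The last column of Table 1 (Protocol Section 1.3) places the phone call "28-35 days after last dose of metformin". Both parts of the table carry this heading. Footnote b gives the purpose: "Phone contact to capture any potential AEs and concomitant treatment(s) and to confirm appropriate contraception usage".
- **Adverse event minimum.** Section 8.3.1 runs active collection from informed consent "through and including a minimum of 28 calendar days after the last administration of the investigational product".
- **Which drugs count.** Section 6.1 names PF-04965842 and metformin as the investigational products.
- **Dosing in Treatment B.** Metformin is given once, on Day 1, and PF-04965842 on Days 1 and 2 (Section 4.1, Table 1). Section 6.1.1 describes the "second dose of PF-04965842 200 mg administered approximately 24 hours after the administration of the first dose". Sequence 1 receives Treatment B in Period 2, and Sequence 2 receives it in Period 1.
- **Status of the schedule.** Section 8 states: "Adherence to the study design requirements, including those specified in the SoA, is essential and required for study conduct".
- **Completion.** Under Section 4.4 a participant has completed the study if "he/she has completed all phases of the study including the last contact phone call".
- **Related obligations.** Contraception for women of childbearing potential (Section 5.1) and collection of pregnancies (Section 8.3.5.1) also run to 28 days after the last product dose.

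**The concern.** The obligations that the call serves are counted from the last dose of investigational product, but the call itself is counted from metformin. The two starting points coincide only when metformin is the last drug given. In Sequence 1 it is not, because PF-04965842 is given again the next day.

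A site can therefore follow the Table 1 heading to the letter and still stop short of the Section 8.3.1 minimum. The call is the only scheduled contact after discharge, so nothing scheduled would pick up the missing day. Section 8.3.1 also releases investigators from actively seeking events once participation has ended.

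At stake is a new adverse event starting on day 28 that nobody asks about, and a last day of contraception use that goes unconfirmed. SAP Section 6.2.1 attributes follow-up events to the treatment taken before, so in Sequence 1 such an event would belong to Treatment B. Primary and secondary pharmacokinetic results are not involved.

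**Working it through.** This is calendar arithmetic on the protocol's own dosing days.

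**Day axis.** Set Period 1 Day 1 = 0 and Day -1 = -1. Table 1 footnote a puts Period 2 Day 1 at least 4 days after Period 1 Day 1; at that minimum, Period 2 Day 1 = 4, Day 2 = 5 and Day 3 = 6.

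**Check of the axis against the plan's figures.**
- Confinement from -1 to 6 is 8 days and 7 nights, as Section 4.1 states.
- PF-04965842 washout in Sequence 2, from Period 1 Day 2 (= 1) to Period 2 Day 1 (= 4), is 4 - 1 = 3 days, as Section 4.1 states.

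**Formula.** Days covered after the last product dose = (last metformin day + call offset) - later of (last metformin day, last PF-04965842 day). The call offset runs from 28 to 35, which is 8 permitted days.

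| Participant | Last metformin | Last PF-04965842 | Call at +28 | Call at +29 | Call at +35 |
|---|---|---|---|---|---|
| Sequence 1 completer | 4 | 5 | 32 - 5 = **27** | 33 - 5 = 28 | 39 - 5 = 34 |
| Sequence 2 completer | 4 | 1 | 32 - 4 = 28 | 33 - 4 = 29 | 39 - 4 = 35 |
| Sequence 2, stops after Period 1 Day 2 | 0 | 1 | 28 - 1 = **27** | 29 - 1 = 28 | 35 - 1 = 34 |

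The Sequence 1 result does not depend on the length of the gap between periods, because both last doses fall in Period 2.

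**How often.** In Sequence 1 the permitted window is PF-04965842 +27 to +34. Seven of its eight days (+28 to +34) meet the minimum. One (+27) misses it by 28 - 27 = 1 day. The documents do not say when within the window calls will be made, so the number short lies between 0 and 6 of the 6 planned Sequence 1 participants. If call days were spread evenly over the window, which is purely an assumption, the expected number would be 6 × 1/8 = 0.75.

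**Pharmacological distance.** Section 4.1 gives a PF-04965842 half-life of about 3-5 hours. Twenty-seven days is 27 × 24 = 648 hours, so 648/5 ≈ 130 to 648/3 = 216 half-lives.

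**After re-timing.** A window of 28 to 35 days from the later last dose gives Sequence 1 calls at PF-04965842 +28 to +35, which is metformin +29 to +36. For Sequence 2 completers the later last dose is metformin, so their window does not move.

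**The case against.** The strongest defence is that the two rules can both be met. Section 1.3 presents Table 1 as an overview and sends the reader to Section 8 for the detail needed to comply. Section 8.3.1 then gives the 28-day minimum, and a site applying both would call Sequence 1 participants on metformin days 29-35, all inside the printed window. The adherence sentence in Section 8 covers Section 8.3.1 as much as the schedule. Section 4.4 defines a completer; it does not say that the call closes the collection period.

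There are also backstops. Known events are followed beyond the active period (Section 8.3.1). Serious events learned of later and thought related must be reported (Sections 8.3.1 and 8.3.1.1). Participants are told to ring at once if contraception stops or pregnancy is suspected (Section 5.3.4). Unplanned visits are allowed (Section 1.3). What remains exposed is essentially a new, non-serious, unreported event starting on day 28 in someone called on the first permitted day.

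Most of this stands. A careful site can avoid the gap, the backstops soften it, and the matter is a mismatch of wording more than a disputed design choice. The defence does not remove the mismatch. No section re-times the call for Sequence 1, and Section 8 itself points back to the schedule for timing. Avoiding the shortfall depends on the site noticing a conflict that the protocol does not flag.

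**Conclusion.** The concern holds, at the lowest level of importance. As written, Table 1 permits a Sequence 1 call 27 days after the last investigational product dose, against a stated minimum of 28. The shortfall is exactly 1 day, on 1 of 8 permitted call days. It could affect anywhere from none to all 6 planned Sequence 1 participants, and also any Sequence 2 participant who stops after the Period 1 Day 2 dose.

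This rests on two readings: that both drugs are investigational products, which Section 6.1 states, and that the roughly 24-hour interval between PF-04965842 doses is one calendar day, which Table 1 shows. The 0.75 figure rests on an even spread of call days that the documents neither support nor rule out, so the range is the safer statement. At 130 to 216 half-lives, a drug-related event first appearing on the missing day is not a serious worry. No estimate, analysis set or pharmacokinetic conclusion changes. The reason to act is that the schedule should not allow a site to miss the protocol's own minimum.

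**What to change.** In both parts of Table 1, change the phone call heading to: *28 to 35 days after the last dose of metformin or PF-04965842, whichever is later*.

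This covers early stoppers in either sequence and leaves Sequence 2 completers as they are. Sections 5.1, 8.3.1 and 8.3.5.1 already count from the last product dose and need no edit. The cost is one heading, printed twice, and a one-day shift of the Sequence 1 call window.
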